#### 10.3.4. α-syn deposits in colon:

 $\alpha$ -syn burden in the colon tissue will be expressed as 1) simply positive or negative, i.e. whether any two slides are positive out of all examined 2) by total percentage of slides examined that are positive 3) by site of highest density of positive  $\alpha$ -syn fibers.

### 10.4. Analysis Plan

#### 10.4.1. **Primary Objective**

The goal of this study is to characterize the distribution of  $\alpha$ -syn pathology through evaluation of quantitative and semi-quantitative outcomes for  $\alpha$ -syn (total, phosphorylated, oligomeric, and other  $\alpha$ -syn species) in multiple tissues and body fluids in individual subjects with clinically typical PD and HC subjects. The primary objectives of the study are to:

- Evaluate the markers of  $\alpha$ -syn as potential surrogate markers for patient selection/enrichment that would be useful in future clinical trials
- Compare  $\alpha$ -syn load in the biofluids and tissues in PD subjects with HC subjects

To address the first objective, the distribution of each  $\alpha$ -syn measurement will be closely examined. The variability of each  $\alpha$ -syn measurement will also be closely examined in an attempt to make recommendations for the optimal measurement to consider in future clinical trials (i.e., the measurement with the lowest variability and, hence, smallest required sample size, to detect clinically important effects of interest).

Two sets of comparisons will be performed to assess the second objective. First, all PD subjects will be pooled and compared to the set of HC subjects with respect to each individual  $\alpha$ -syn measurement. Then, subjects in each of the three separate PD groups will be compared to the healthy controls.

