An important question that this study aims to address is what tissue or body fluid offers the most promising measure of  $\alpha$ -syn load to determine if any of these tissue or biofluid sampling methods prove useful biomarkers for future use in therapeutic studies, particularly for those with disease modifying potential. The blood and saliva sampling procedures to be utilized as part of this study are of low risk and easily obtained. While collecting CSF is a more invasive procedure, this procedure is now being widely used for studies evaluating biomarkers for neurodegenerative diseases, including PD. The variability in the performance of the assays for measuring  $\alpha$ -syn species in these biofluids is a major limitation. Evaluation of  $\alpha$ -syn in peripheral tissues has the potential for more reliable outcomes. The tissue biopsies to be obtained as part of these studies involve routine biopsy procedures of peripheral tissues. Skin biopsies and sigmoid colon biopsies are procedures that are already performed routinely as part of preventive care in a large portion of the population. While submandibular gland biopsies are less frequently performed, the safety data in 40 PD subjects and 10 HCs undergoing biopsy have resulted in AEs mainly limited to swelling and bruising at the biopsy site (Adler et al 2015). In addition, given that the current literature suggests that α-syn pathology might begin in peripheral tissues in the pre-motor stage of disease and then move centrally to involve the central nervous system (CNS), understanding the peripheral  $\alpha$ -syn burden may ultimately be key to the development of treatments to prevent progression into the CNS.

While all studies conducted thus far have utilized small sample sizes evaluating single biofluid or tissue types and using a variety of methodologies for sample collection, processing and analysis, the Systemic Synuclein Sampling Study (S4) design provides the opportunity to evaluate  $\alpha$ -syn species in multiple tissues and biofluids within the same subject. S4 will also employ standardized collection, processing and analysis methodology across sites, making this the largest PD cohort evaluated for *in vivo* tissue sampling. Understanding the  $\alpha$ -syn burden along the spectrum of disease severity (early untreated to advanced disease) will inform the next steps for utilizing these markers in the drug development process.

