# 2. STUDY OBJECTIVES

# 2.1. Primary Objective

The goal of this study is to characterize the distribution of  $\alpha$ -syn pathology through evaluation of quantitative and semi-quantitative outcomes for  $\alpha$ -syn (total, phosphorylated, oligomeric and other  $\alpha$ -syn species) in multiple tissues and body fluids in individual subjects with clinically typical PD and HC. The primary objectives for this study are as follows:

- To evaluate the  $\alpha$ -syn markers as potential surrogate markers for patient selection/enrichment that would be useful in future clinical trials.
- To compare  $\alpha$ -syn load in the biofluids and tissues in PD subjects with HC subjects

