## 10.3. Study Outcome Measures

### 10.3.1. **Biofluid** α-syn levels:

Whole blood, serum, plasma, saliva, and CSF  $\alpha$ -syn will be analyzed using the most optimal, currently available, quantitative and semi-quantitative assays. The outcome will be expressed as a concentration of total  $\alpha$ -syn and other  $\alpha$ -syn species or a ratio of specific species to total levels.

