### 10.3.2. α-syn deposits in skin:

 $\alpha$ -syn burden in skin biopsies will be expressed as 1) simply positive or negative, i.e. whether any two slides are positive out of all examined 2) by total percentage of slides examined that are positive 3) by site of highest density of positive  $\alpha$ -syn fibers.

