### **10.5.** Sample Size Justification

As this is an exploratory trial, it is difficult to obtain solid estimates for key parameters of interest. However, the PPMI study provides data in an early PD cohort that can be used for the purposes of assessing the "effects" that this study may be powered to detect. In the PPMI cohort of early PD subjects, the mean baseline CSF levels of total  $\alpha$ -syn was equal to  $1845 \pm 770$  pg/ml. With a sample size of 20 subjects per group, and assuming a significance level of 0.05, we will have 80% power to detect a difference of 40% or more between HCs or one of the later PD cohorts versus the early PD cohort. Similarly, the study will have 90% power to detect a difference of 50% or more between HCs or one of the later PD cohort.

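### Section 10.4.1 treats the lowest-variability marker as the one needing the smallest sample, which does not follow and leaves PD–HC separation out of the recommendation

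*Protocol*

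**What the plan says.** Protocol section 2.1 sets as the first primary objective the evaluation of α-synuclein markers as "potential surrogate markers for patient selection/enrichment that would be useful in future clinical trials". Section 1.2 says the study is meant to show "what tissue or body fluid offers the most promising measure of" α-synuclein burden.

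Section 10.4.1 says how this objective will be met. The distribution and variability of each measurement will be examined so as to recommend an optimal one, which it explains as "the measurement with the lowest variability and, hence, smallest required sample size, to detect clinically important effects of interest". No other criterion for the recommendation is given.

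The second primary objective, in the same section, compares groups on each measurement: "First, all PD subjects will be pooled and compared to the set of HC subjects", followed by each PD stage against controls. Nothing connects those comparisons to the choice of optimal measurement.

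The measurements are of several kinds. Under section 10.3.1 a biofluid result is a concentration or "a ratio of specific species to total levels". Under sections 10.3.2 to 10.3.4 a tissue result is "simply positive or negative, i.e. whether any two slides are positive out of all examined", or a percentage of positive slides, or the site of highest fibre density.

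**The concern.** The word linking low variability to small sample size carries the whole criterion, and the link holds only when every marker is expected to show the same effect on the same scale. The protocol does not state that condition, and its own mix of outcome types rules it out for raw variability.

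The purpose makes the gap more important. A marker for selecting or enriching patients has to tell PD from non-PD. The stated criterion contains no difference, no standardised effect and no measure of discrimination. Followed literally, it could put forward a precise but uninformative marker over one that separates the groups. That would be an unsound answer to a primary objective, from subjects who had undergone a lumbar puncture and three kinds of biopsy.

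**Working it through.** **Inputs.** From section 10.5: CSF total α-synuclein in early PD, mean 1845 and SD 770 pg/ml; 20 per group; significance level 0.05; differences of 40% (80% power) and 50% (90% power). From section 3.3.1: target of 60 PD subjects and 20 controls. From section 1.1: published positivity rates by tissue. Sidedness is not stated; I assume two-sided.

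**1. The plan's own figures.** CV = 770/1845 = 0.417.
- 40% difference: 0.40 × 1845 = 738 pg/ml, d = 738/770 = 0.958. Power with 20 per group (t-test) is 84.0%, against 80% stated.
- 50% difference: 922.5 pg/ml, d = 1.198. Power is 95.8%, against 90% stated.
- The differences detectable with 20 per group are 37.9% (80% power) and 43.9% (90% power).

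The stated figures are therefore not reproduced exactly, but they err on the cautious side and do not affect this point. What matters is that section 10.5 uses both a difference and an SD, as any such calculation must.

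**2. What sample size depends on.** In the normal approximation, n per group = 2(1.960 + 0.842)² × (SD/difference)² for 80% power. SD enters only through its ratio to the difference.

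**3. Where the inference would hold.** Fix the relative difference at 40% for every marker. CV 0.417 then needs 18 per group and CV 0.20 needs 4 (normal approximation). Lower variability does give a smaller sample in that case.

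**4. Where it fails.** Let the difference vary. All rows below the first are assumptions, chosen to show a range.

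| Marker | CV | PD–HC difference | d | n per group, 80% power |
|---|---|---|---|---|
| CSF, protocol figures | 0.417 | 40% | 0.958 | 18 (normal), 19 (t-test) |
| Hypothetical | 0.10 | 2% | 0.20 | 394 (t-test) |
| Hypothetical | 0.20 | 5% | 0.25 | 252 (normal) |
| Hypothetical | 0.20 | 10% | 0.50 | 63 (normal) |
| Hypothetical | 0.20 | 15% | 0.75 | 28 (normal) |
| Hypothetical | 0.20 | 20% | 1.00 | 16 (normal) |

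By lowest CV, every hypothetical row is preferred to CSF, yet four of the five need more subjects. A marker with CV 0.20 needs fewer than CSF only if its difference exceeds 0.20 × 0.958 = 19.2%. With CV 0.10 the threshold is 0.10 × 0.958 = 9.6%.

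**5. Scale.** Writing the CSF result in ng/ml changes the SD from 770 to 0.770 and leaves n at 18. Raw SD cannot rank markers measured in different units.

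**6. Positive/negative calls.** The variance is p(1 − p).
- Negative in everyone: zero in PD and in controls.
- Positive in everyone, controls included: zero in both.
- Positive in all PD and no controls: also zero in both.

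Within-group variance cannot tell the perfect marker from the two useless ones. If variability is taken over all 80 subjects instead, the perfect marker has 0.75 × 0.25 = 0.1875 and the useless ones have 0, so the rule prefers a useless one.

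**The case against.** The strongest defence is that the parenthesis ends with clinically important effects. For a given effect, lower variability does mean fewer subjects (step 3). This would rescue the sentence if a common effect on a common scale were specified, but none is. Variability is also left undefined, and an analysis plan could supply a scale-free version such as the CV. That would answer step 5 but not step 4.

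It is also fair to say that the study is exploratory, that the text speaks only of an attempt at recommendations, and that no enrolment or stopping decision depends on it. PD and control subjects will be compared on every measurement, including early PD against controls, so it would be wrong to say that the study ignores group separation. These points limit the consequence. They do not correct the criterion, because no text ties those comparisons to the recommendation.

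A reader might infer that the rule would pick a poor tissue in this study. The cited rates do not show that. For the sampled tissues, section 1.1 reports PD positivity of 100% for cervical skin, 90% for sigmoid colon and 89.5% for submandibular gland (the last post-mortem). The variances within PD are 0, 0.9 × 0.1 = 0.090 and 0.895 × 0.105 = 0.094. Lowest variance picks skin, for which the same source reports no positive controls. The 1-in-15 rate for minor salivary gland, also in section 1.1, looks like a counterexample, but this study does not sample that tissue.

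A reader might also fault the absence of paired comparisons between markers within a subject. Such methods commonly belong to an analysis plan, which is not at hand, so that is not an error in this section.

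**Conclusion.** The point stands as an error in a stated criterion: lowest variability does not imply smallest required sample size, and across these outcome types it cannot rank the markers. The formula alone establishes this. The contrast of about 394 against about 19 per group shows how far the ranking can go wrong; it rests on an assumed marker (CV 10%, difference 2%), two-sided 0.05 and 80% power.

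The documents do not support the stronger conclusion that an uninformative marker will be recommended. They support only that the rule as written could not prevent it. I rate this as should-fix. Sampling, sample size, safety and the planned PD–HC tests are untouched, and a sound ranking can be computed from the same data.

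**What to change.** Replace the parenthesis in section 10.4.1 so that the recommendation rests on separation of PD from controls:

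- for continuous measures, the standardised PD–HC difference (the quantity that drives sample size) and the ROC area with 95% confidence interval;
- for positive/negative tissue calls, sensitivity and specificity with exact 95% confidence intervals;
- each for pooled PD and for early PD against controls, matching comparisons that the section already plans;
- variability reported descriptively, not as the ranking criterion.

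The cost is a change of wording and a modest amount of extra analysis. No new data, visits or subjects are needed.

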## 3.3.2. Inclusion Criteria for PD Subjects

• Male or female age 40 or older at the time of PD diagnosis.

- Clinical diagnosis of PD based on bradykinesia plus one of the following: rest tremor or rigidity.
- DAT deficit at screening based on visual interpretation of DaTSCANTM imaging.
- PD subjects will need to fall into one of the following stages:
  - Early untreated PD not requiring dopamine replacement medication (anticholinergics, MAO-B inhibitors and amantadine permitted), Hoehn and Yahr 1-2, < 2 years from diagnosis.
  - Moderate PD responsive and currently treated with dopamine replacement therapy without evidence of motor fluctuations or dyskinesias.
  - Advanced PD with motor fluctuations or dyskinesias, > 5 years from diagnosis.
- Ability to provide written informed consent in accordance with Good Clinical Practice (GCP), International Conference on Harmonization (ICH), and local regulations.
- Willing and able to comply with scheduled visits, required study procedures and laboratory tests.

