# 3.3.3. Inclusion Criteria for HC Subjects

- Male or female age 50 or older at the time of the screening visit
- Ability to provide written informed consent in accordance with GCP, ICH, and local regulations.
- Willing and able to comply with scheduled visits, required study procedures and laboratory tests.

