### 3.3.7. Enrollment Monitoring for Age, Gender and Disease Stage

Enrollments will be monitored centrally by the Steering Committee (SC) with the goal of achieving age and gender balance across the PD and HC subjects. In addition, the PD enrollment will be monitored for stage to ensure that the three stages (early untreated, moderate and advanced) are equally represented. Sites will be instructed if recruitment restrictions need to be implemented as the study progresses in order to maintain a balanced population and obtain the appropriate PD subjects.

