#### 10.4.2. Secondary Objective:

**Feasibility & Safety:** One important secondary objective is to evaluate the feasibility and safety of obtaining multiple tissues and biofluids in an individual with PD. Feasibility will be assessed by tabulating the percentage of subjects in each group who provide complete samples. The assessment of safety will be based primarily on the frequency of procedure related AEs. All AEs will be coded using the Medical Dictionary for Regulatory Authorities (MedDRA). Procedure related AEs will be summarized by system organ class and preferred term. We will examine safety across groups in two different ways. First, the percentage of subjects who experience any procedure related AEs will be compared across groups using a chi-square test. Additionally, the rates of procedure related AEs will be compared using a Generalized Linear Model with a Poisson link.

**Compare**  $\alpha$ -syn Load Across PD Groups: Another important secondary objective is to compare the  $\alpha$ -syn load among the tissues and fluids in the PD cohort subdivided by the clinical stage of disease (early PD not requiring dopamine replacement therapy, moderate PD on

dopamine replacement therapy without motor fluctuations, advanced PD with motor fluctuations). To address this objective, trend tests (continuous or categorical, as appropriate) will be performed to assess  $\alpha$ -syn levels across the three cohorts of PD subjects.

**Compare**  $\alpha$ -syn Load with DAT Imaging: Another important secondary objective is to compare the  $\alpha$ -syn load among the tissues and fluids with disease severity based on striatal degeneration measured by DAT imaging across the PD groups in addition to comparing PD and HC groups. To accomplish this objective, each measure of  $\alpha$ -syn load will be correlated with DAT imaging data using an appropriate Generalized Linear Model.

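### Age floors that leave PD subjects aged 40-49 without an eligible control, and a balance goal that states no age or sex target by stage, leave the stage contrasts open to confounding by age

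*Protocol*

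**What the plan says.** **Eligibility.** Section 3.3.3 admits controls who are "Male or female age 50 or older at the time of the screening visit". Section 3.3.2 admits PD subjects who are "Male or female age 40 or older at the time of PD diagnosis" and sets no age floor at screening. It defines early PD by "Hoehn and Yahr 1-2, < 2 years from diagnosis" among other conditions, and the third stage as "Advanced PD with motor fluctuations or dyskinesias, > 5 years from diagnosis". Moderate PD has no limit on time since diagnosis.

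**Enrolment control.** Section 3.3.7 has the Steering Committee monitor enrolment centrally "with the goal of achieving age and gender balance across the PD and HC subjects". For stage, "the PD enrollment will be monitored for stage to ensure that the three stages (early untreated, moderate and advanced) are equally represented". Sites can be told to restrict recruitment to keep the population balanced. No matching rule, tolerance, or age or sex target by stage is given.

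**Comparisons.** Under section 10.4.1, "all PD subjects will be pooled and compared to the set of HC subjects with respect to each individual" α-syn measurement, and each of the three PD groups is then compared with HC. Under section 10.4.2, "trend tests (continuous or categorical, as appropriate) will be performed to assess" α-syn levels across the three PD cohorts. The enrolment goal in section 3.3.1 is 20 subjects per PD stage and 20 HC. Date of birth and gender are collected on everyone (section 5.1.1).

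**The concern.** This is a non-randomised, cross-sectional comparison. If a marker varies with age or sex and the groups differ in age or sex, part of that variation is read as an effect of disease or stage. The protocol treats both factors as relevant, since it monitors them centrally. Its reference list also carries a title linking lower CSF α-syn to ageing, although a title gives no slope.

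Two things that the protocol itself fixes sit badly with its balance goal. The age floors differ by ten years and are measured at different moments, so the youngest PD subjects cannot be balanced by controls of their own age. And the stated goal concerns PD against HC, whereas several planned contrasts are stage against HC or stage against stage. At stake are the stage-HC comparisons, which belong to a primary objective, and the stage trend, which is secondary. Both are meant to inform the choice of markers for later trials.

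**Working it through.** **1. Lowest possible age at screening, from sections 3.3.2 and 3.3.3**

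| Group | Floor in the text | Time since diagnosis | Lowest age at screening |
|---|---|---|---|
| HC | 50 at screening | not applicable | 50 |
| Early PD | 40 at diagnosis | under 2 years | about 40 |
| Moderate PD | 40 at diagnosis | no limit | about 40 |
| Advanced PD | 40 at diagnosis | over 5 years | above 45 |

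PD subjects aged 40-49 can enter in every stage (in advanced PD only from above 45). No control of that age can.

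**2. Balance overall does not secure balance by stage.** Suppose early PD averages 5 years younger than HC, moderate PD the same age, and advanced PD 5 years older, with equal numbers. The mean PD-HC gap is (-5 + 0 + 5)/3 = 0, so the stated goal is met on average. Yet two of the three stage-HC contrasts carry a 5-year gap, and the early-to-advanced gap is 10 years. These gaps are invented to show the mechanism; the protocol gives none.

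**3. The protocol's own power figures (section 10.5).** Inputs: mean 1845 and SD 770 pg/ml, 20 per group, level 0.05, taken as two-sided because the text does not say.
- 40% difference: 0.40 × 1845 = 738; 738/770 = 0.958 SD. Power is 84.0% by the t distribution (85.8% normal), against a stated 80%.
- 50% difference: 922.5/770 = 1.198 SD. Power is 95.8% (96.6% normal), against a stated 90%.

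The stated figures are not reproduced exactly; they are somewhat conservative. That is not the point here. The calculation takes the groups as comparable and includes no covariates.

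**4. Illustration of the error rate.** Assumed, not from the protocol: the marker changes by 0.01-0.03 SD per year and two groups differ by 5-10 years.
- Bias = slope × gap: from 0.01 × 5 = 0.05 SD to 0.03 × 10 = 0.30 SD.
- On the CSF scale: 0.05 × 770 = 38.5 pg/ml (2.1% of 1845) to 0.30 × 770 = 231 pg/ml (12.5%).
- Unadjusted two-sided t-test, 20 v 20, 38 degrees of freedom, noncentrality = bias × √(20 × 20/40) = bias × √10.

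| Bias (SD) | Actual error at nominal 5% |
|---|---|
| 0.05 | 5.3% |
| 0.10 | 6.1% |
| 0.15 | 7.5% |
| 0.20 | 9.5% |
| 0.30 | 15.2% |

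In the pattern of step 2, each 5-year stage-HC gap gives 0.05-0.15 SD, hence 5.3-7.5%. The early-advanced gap of 10 years gives 0.10-0.30 SD. The trend test was not calculated separately. With equal groups and equally spaced scores, a linear trend rests on the advanced-minus-early difference, so its exposure should be close to the 20 v 20 rows.

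**5. Price of adjustment.** For 20 v 20 and the 40% difference, with age and sex in the model (36 degrees of freedom), let ρ be the age-marker correlation and g the age gap in SDs.
- Effective difference = 0.958 × √(1 - r²)/√(1 - ρ²), where r² = 0.25g²/(1 + 0.25g²).
- At g = 1, r² = 0.25/1.25 = 0.20. The effective difference is 0.857 SD at ρ = 0 and 0.935 SD at ρ = 0.4. Power is 75% and 82%.
- At g = 0.5, power is 82-88%. With no gap it is 84-90%.

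The unadjusted figure is 84%, and it assumes no confounding.

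**The case against.** The strongest reply is that covariates are normally left to the statistical analysis plan, which is not shown. A reader might infer from the wording that the protocol commits to unadjusted contrasts. It does not. Section 10.4.1 says who is compared with whom and names no test, and section 10.4.2 leaves the trend test open. The t-test and chi-square sentence in section 10.2 concerns demographic and clinical characteristics. Missing adjustment alone would therefore not be a finding. What stands is that age floors and enrolment targets are protocol matters, and no later analysis can supply controls under 50.

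A reader might also infer that balance is sought only for PD taken as one group. Section 3.3.7 does not say so. It does not exclude balance within stage, and the power to restrict recruitment is a real safeguard. It simply states no such target.

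Nor does the text show that the stages will differ in age. It limits time since diagnosis, not current age: an early subject may be diagnosed late in life and an advanced one in the mid-forties. A gap is plausible, not certain.

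Finally, the same bias range applied to the 60 v 20 contrast gives errors up to 20.9%. That figure should not be relied on, because it places a 5-10 year gap in the very contrast that section 3.3.7 already aims to balance. Even 0.30 SD is about a third of the 0.91 SD detectable with 80% power at 20 v 20, and the study is expressly exploratory.

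**Conclusion.** The point holds as a design weakness of modest and unknown size. Two parts rest on the text alone: the eligibility floors leave PD subjects aged 40-49 with no age-eligible control, against the protocol's own balance goal; and that goal sets no age or sex target by stage, although stage contrasts and a stage trend are planned. That stages may differ in age is a reasonable expectation from their definitions, not a stated fact.

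The 5-15% error range is an illustration that rests on assumed slopes and gaps and on an unadjusted two-sided test. At the low end the effect is negligible; at the high end it would matter. The documents do not show that any PD-HC comparison is in fact biased. The point is worth acting on because the remedy is cheap.

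**What to change.** 1. **Section 3.3.7.** Extend the existing Steering Committee monitoring of age and gender to each PD stage against HC. Reconcile the PD and HC age bases, either by using the same reference point for age or by frequency-matching HC to the PD age distribution.
2. **Sections 10.4.1 and 10.4.2.** State that the PD-HC, stage-HC and stage-trend comparisons are adjusted for age at sampling and sex, with the unadjusted result alongside. Add a sensitivity analysis restricted to the age range shared by PD and HC, because below 50 regression only extrapolates for controls.

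The form of each model can stay with the analysis plan. Any model for the proportion of positive slides should allow for clustering of slides within subject.

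**Cost.** Wording changes, two degrees of freedom per model and a mild recruitment constraint; the data are already collected. If the age gap were as large as 1 SD, power at the 40% difference would be about 75-82% against 84%. Age adjustment does not separate stage from disease duration, so the trend would still need cautious reading.

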# **3.3.** Study Population

## 3.3.1. Subject Numbers

Up to 100 subjects will be enrolled in this study. Subjects are considered enrolled in the study if they complete screening and are found to be eligible based on the inclusion and exclusion criteria. The enrollment goal for this study is 80 subjects (20 early PD not requiring dopamine replacement therapy, 20 moderate PD on dopamine replacement therapy without motor fluctuations, 20 advanced PD with motor fluctuations, 20 HC subjects) that complete at least 2 biofluid samplings (blood, saliva and CSF) and at least 2 tissue samplings (skin, colon, submandibular gland).

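### Section 10.4.1 picks the least variable alpha-syn measure and ties its sample size to the same data, so the winner's SD is too low

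*Protocol*

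**What the plan says.** Section 10.3 defines the measures. The fluids are "Whole blood, serum, plasma, saliva, and CSF", each reported as total alpha-syn, other species, or ratios of species to total. Skin, submandibular gland and colon are each expressed in three ways: positive or negative, percentage of positive slides, and site of highest fibre density.

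Section 10.4.1 then gives two uses of these measures.

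- For the first primary objective, the distribution and variability of every measure are examined in order to "make recommendations for the optimal measurement to consider in future clinical trials". A parenthesis defines the optimal one as the least variable, and equates this with needing the fewest subjects to detect effects of interest.
- For the second, "all PD subjects will be pooled and compared to the set of HC subjects with respect to each individual" measurement, after which "subjects in each of the three separate PD groups will be compared to the healthy controls".

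Section 3.3.1 sets the target at 20 per group, including "20 advanced PD with motor fluctuations, 20 HC subjects". Section 10.4 states no significance level. The only one in the protocol is in the sample-size text (Synopsis and section 10.5): "With a sample size of 20 subjects per group, and assuming a significance level of 0.05".

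**The concern.** Each measure's SD is estimated with error. Choosing the smallest estimate tends to choose a measure whose SD happened to come out low, so its reported SD is on average below its true value. Section 10.4.1 then reads that figure as a smaller required sample size, and required sample size is proportional to the variance. Selecting a measure to carry into later trials is a primary objective, so an underpowered later trial is the cost.

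The second objective raises a smaller matter. Many comparisons are made against one set of 20 controls, so some would reach significance by chance. A chance deviation in the control mean would also appear in all three stage comparisons at once.

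**Working it through.** **The plan's own figures.** The protocol states no figure for the selection step. Its only calculation is power for CSF total alpha-syn in section 10.5: "assuming a significance level of 0.05, we will have 80% power to detect a difference of 40% or more", and 90% for 50%. Inputs are mean 1845, SD 770 and 20 per group. A 40% difference is 0.40 × 1845 = 738, or 738/770 = 0.96 SD, which gives 84.0% power by two-sided t-test. A 50% difference gives 95.8%. The stated powers are conservative and do not bear on this point.

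**Number of candidates.** Five fluids (total alpha-syn only) plus 3 tissues × 3 expressions = 14. If site of highest density is not a testable quantity, 5 + 3 × 2 = 11. Other species and ratios would add to either count.

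**Bias in the winner's variance.** Simulation: 14 normal measures on a common scale, common pairwise correlation, the measure with the smallest sample SD chosen, and its sample variance divided by its true variance.

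| Subjects | True SDs | Correlation | Mean variance ratio | Understated by |
|---|---|---|---|---|
| 60 | equal | 0 | 0.712 | 29% |
| 60 | equal | 0.3 | 0.723 | 28% |
| 60 | equal | 0.6 | 0.765 | 24% |
| 60 | equal | 0.9 | 0.869 | 13% |
| 60 | 0.9 to 1.1 | 0 | 0.751 | 25% |
| 60 | 0.7 to 1.3 | 0 | 0.859 | 14% |
| 60 | 0.5 to 1.5 | 0 | 0.933 | 7% |

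For SDs of 0.5 to 1.5, the shortfall falls towards 0 as correlation rises. With 11 equal-SD measures it is 24 to 27% at correlations up to 0.5. The protocol does not say in which subjects variability is judged. In a single group of 20, the equal-SD shortfall is 22 to 47%.

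**Effect on the next trial.** Size per arm is n = 2(z₁₋α/₂ + z₁₋β)²σ²/δ², so planned n divided by needed n equals the variance ratio. A trial needing 100 per arm would be planned at 71 (ratio 0.712), 87 (0.869) or 93 (0.933). True power for a planned 80% at two-sided 0.05 is Φ(2.80 × √ratio − 1.96):

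- ratio 0.712: Φ(2.80 × 0.844 − 1.96) = Φ(0.40), about 66%
- ratio 0.869: Φ(2.80 × 0.932 − 1.96) = Φ(0.65), about 74%
- ratio 0.933: Φ(2.80 × 0.966 − 1.96) = Φ(0.74), about 77%

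**Secondary point.** Four comparisons per measure give 11 × 4 = 44 to 14 × 4 = 56. If no measure differed and each were tested at 0.05, 44 × 0.05 = 2.2 to 56 × 0.05 = 2.8 false positives are expected. With 14 measures, the chance of at least one is 86% at correlation 0 and 34% at 0.9. For one measure, two or more stages are falsely significant 2.2% of the time with shared controls. Three independent tests would give 3 × 0.05² × 0.95 + 0.05³ = 0.7%.

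**The case against.** The study is declared exploratory, and only the protocol is at hand. Multiplicity rules are commonly left to the SAP, and strict error control is debatable here. That stands, which is why the PD versus HC comparisons support no more than a request for labelling. The null in which no measure differs also sits poorly with the strong tissue contrasts cited in section 1.1, although other results cited there conflict.

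Three stronger readings are tempting, and the document does not support them.

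- A reader might infer that every measure is tested at 0.05. Section 10.4 sets no level; 0.05 appears only for the CSF sample size.
- A reader might infer that chance PD versus HC differences drive the recommendation and inflate the winner's difference. The stated criterion is variability. In simulation under that rule with a true difference of 0.5 SD, the chosen measure's raw difference averages 0.49 to 0.51, so it is unbiased. Only the standardised difference rises, to 0.56 to 0.59, because its SD is too small.
- A reader might infer that the same bias follows from any ranking criterion. The previous item shows that it does not: what is biased depends on what is ranked.

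The size of the SD bias is also open to challenge. Equal true SDs are close to a worst case. The three expressions per tissue come from the same slides and may be highly correlated, and the measures mix concentrations, percentages and binary results. This is why a range is given. Finally, the protocol speaks of an attempt at recommendations and does not commit to sizing a trial on the winner's SD. It does, however, equate lowest variability with smallest required sample size, and that is the step that needs correcting.

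**Conclusion.** The point holds for the selection rule that section 10.4.1 actually states. Choosing the lowest observed variability among at least 11 to 14 measures and reading a sample size from it in the same subjects understates the winner's variance. With 60 PD subjects the understatement is about 13 to 29% for equal true SDs (correlation 0.9 to 0) and about 0 to 7% for true SDs of 0.5 to 1.5. A trial sized on that SD would be too small by about the same fraction. These figures assume normal data on a common scale, with correlations and true SDs that the protocol does not give.

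The comparisons with the 20 shared controls are a secondary matter of presentation. The 2.2 to 2.8 expected false positives depend on no measure differing and on testing each at 0.05, and neither is stated in the plan.

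**What to change.** In section 10.4.1, add that the choice of the optimal measure will be repeated inside a bootstrap:

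1. Resample subjects within group, recompute every measure's variability on the scale used for ranking, and choose again.
2. In each resample, compare the chosen measure's SD with the SD of that same measure in the full data. The average discrepancy is the optimism.
3. Report the optimism-corrected SD of the recommended measure and how often each measure is chosen.
4. Use only the corrected SD in any statement about future sample size.

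Also state that the PD versus HC comparisons, if unadjusted, are exploratory, and that agreement between stages is not independent confirmation because the controls are shared.

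The cost is modest analysis time and a less favourable figure for the recommended measure. The bootstrap removes most, not all, of the bias where it is large, and over-corrects slightly (about 4 to 5% of variance) where the measures differ widely. No new data are needed.
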